
What does "wake up tired" mean to you?
	
Do you experience this as part of your nasal polyps?
 
Why did you choose an answer of [X]?
 
Would your score be different if you were asked to rate the severity and frequency of "waking up tired" separately, rather than together? Why?
 
What would your severity based and frequency based scores be?
		
How easy or difficult was it for you answer this question? Why?
 
What change in score would make a difference to you and why?

[QUESTION 17] Fatigue			

What does fatigue mean to you?
 
Would you use any other words to describe this term?
 
Is "fatigue" and "waking up tired" the same or different? Why?
	
Do you experience this as part of your nasal polyps?
 
Why did you choose an answer of [X]?
 
Would your score be different if you were asked to rate the severity and frequency of your "fatigue" separately, rather than together? Why?
 
What would your severity based and frequency based scores be?
		
How easy or difficult was it for you answer this question? Why?
 
What change in score would make a difference to you and why?

ADELPHI VALUES

Understanding	Relevance	Recall period	Response Options
[QUESTION 18] Reduced productivity			

What does “reduced productivity” mean to you? Would you use any other words to describe this term?
	
Do you experience this as part of your nasal polyps? Why did you choose an answer of [X]? Would your score be different if you were asked to rate the severity and frequency of your “reduced productivity” separately, rather than together? Why? What would your severity based and frequency based scores be?
		
How easy or difficult was it for you answer this question? Why? What change in score would make a difference to you and why?

[QUESTION 19] Reduced concentration			

What does “reduced concentration” mean to you? Would you use any other words to describe this term? Is “reduced concentration” the same or different to “reduced productivity”? Why?
	
Do you experience this as part of your nasal polyps? Why did you choose an answer of [X]? Would your score be different if you were asked to rate the severity and frequency of your “reduced concentration” separately, rather than together? Why? What would your severity based and frequency based scores be?
		
How easy or difficult was it for you answer this question? Why? What change in score would make a difference to you and why?

[QUESTION 20] Frustration/restless/irritable			

What does “frustration” meant to you? What does “restless” mean to you? What does “irritable” mean to you? Would you use any other words to describe these words? Are these terms the same or different? Why?
	
Do you experience this as part of your nasal polyps? Why did you choose an answer of [X]? Would your score be different if you were asked to rate “frustration”, “restlessness” and “irritability” separately? What scored would they be? Would your score be different if you were asked to rate the severity
		
How easy or difficult was it for you answer this question? Why? What change in score would make a difference to you and why?

ADELPHI VALUES

Understanding	Relevance	Recall period	Response Options
	and frequency of your “frustration” separately, rather than together? Why? What would your severity based and frequency based scores be?		
[QUESTION 21] Sad			
What does “sad” mean to you? Would you use any other words to describe this term?	Do you experience this as part of your nasal polyps? Why did you choose an answer of [X]? Would your score be different if you were asked to rate the severity and frequency of your “sadness” separately, rather than together? Why? What would your severity based and frequency based scores be?	What time frame were you thinking about when answering this question? Was it easy or difficult to remember over the past 2 weeks? Did you think about how bad the impact is and how often you experience it? Why/Why not?	How easy or difficult was it for you answer this question? Why? What change in score would make a difference to you and why?
[QUESTION 22] Embarrassed			
What does “embarrassed” mean to you? Would you use any other words to describe this term?	Do you experience this as part of your nasal polyps? ? Why did you choose an answer of [X]? Would your score be different if you were asked to rate the severity and frequency of your “sadness” separately, rather than together? Why? What would your severity based and frequency based scores be?		How easy or difficult was it for you answer this question? Why? What change in score would make a difference to you and why?

**General feedback on SNOT-22**

ADELPHI VALUES

🗨️ *We would also like to have your feedback on the questionnaire overall.*

**28. What do you think of the questionnaire in general?**

- *What did you like/dislike about the questionnaire?*
- *What did you find easy/difficult*

**29. Are there any symptoms or impacts that you experience due to your nasal polyps that you feel are missing from the questionnaire?**

**30. Do you have any further comments about this questionnaire that we haven't already discussed?**

Date:  /  / 2017  
MM DD

Center Number: /\_\_\_/\_\_\_/

Participant N°: /\_\_\_/\_\_\_/

• Cognitive debriefing of VAS scales

ADELPHI VALUES

Understanding	Relevance	Recall period	Response Options

[NASAL OBSTRUCTION VAS] ‘Please rate your nasal obstruction at its worst over the previous 24 hours’  [SCALE] 0 (none) – 100 (as bad as you can imagine)
			

What does “nasal obstruction” mean to you?            Would you use any other words to describe this term?            What does “at its worst mean to you”?            “What does “over the previous 24 hours mean to you”?            What does “0 none” mean to you?            What does “100 as bad as you can imagine none” mean to you?
	
Do you experience this as part of your nasal polyps?            Please mark your answer on the line.            What number from 0-100 does this line represent?            Does the severity of your nasal obstruction differ over 24 hours?
	
What time frame were you thinking about when answering this question?            Was it easy or difficult to remember over the past 2 weeks?
	
How easy or difficult was it for you answer this question? Why?            What change in score would make a difference to you and why?

[NASAL DISCHARGE VAS] ‘Please rate your nasal discharge at its worst over the previous 24 hours’  [SCALE] 0 (none) – 100 (as bad as you can imagine)
			

What does “nasal discharge” mean to you?            Would you use any other words to describe this term?
	
Do you experience this as part of your nasal polyps?            Please mark your answer on the line.            What number from 0-100 does this line represent?
		
How easy or difficult was it for you answer this question? Why?            What change in score would make a difference to you and why?

Date:  /  / 2017  
MM DD

Center Number: /\_\_\_/\_\_\_/

Participant N°: /\_\_\_/\_\_\_/

ADELPHI VALUES

Understanding	Relevance	Recall period	Response Options

[MUCUS IN THROAT VAS] 'Please rate the feeling of mucus in the throat at its worst over the previous 24 hours'  [SCALE] 0 (none) – 100 (as bad as you can imagine)
			

What does “mucus in the throat” mean to you?            Would you use any other words to describe this term?
	
Do you experience this as part of your nasal polyps?            Please mark your answer on the line.            What number from 0-100 does this line represent?            Does your experience of mucus in throat change in severity over 24 hours?
	
What time frame were you thinking about when answering this question?            Was it easy or difficult to remember over the past 2 weeks?
	
How easy or difficult was it for you answer this question? Why?            What change in score would make a difference to you and why?

[LOSS OF SMELL VAS] 'Please rate your loss of smell at its worst over the previous 24 hours'  [SCALE] 0 (none) – 100 (as bad as you can imagine)
			

What does “loss of smell” mean to you?
	
Do you experience this as part of your nasal polyps?            Please mark your answer on the line.            What number from 0-100 does this line represent?            Does your experience of loss of smell change in severity over 24 hours?
		
How easy or difficult was it for you answer this question? Why?            What change in score would make a difference to you and why?

[FACIAL PAIN VAS] 'Please rate your facial pain or pressure at its worst over the previous 24 hours'  [SCALE] 0 (none) – 100 (as bad as you can imagine)
			
	
Do you experience this as part of your nasal polyps?            Please mark your answer on the line.            What number from 0-100 does this line represent?
		
How easy or difficult was it for you answer this question? Why?            What change in score would make a difference to you and why?

Date:  /  / 2017  
MM DD

Center Number: /\_\_\_/\_\_\_/

Participant N°: /\_\_\_/\_\_\_/

ADELPHI VALUES

Understanding	Relevance	Recall period	Response Options

[OVERALL VAS SYMPTOM SCORE] ‘Overall, please rate your nasal polyps symptoms at their worst over the previous 24 hours’
 
[SCALE] 0 (none) – 100 (as bad as you can imagine)
			

What does “overall symptoms” mean to you? Do you prefer the wording of this question, or the previous question? Why?
	
Do you experience this as part of your nasal polyps? Please mark your answer on the line. What number from 0-100 does this line represent?
		
How easy or difficult was it for you answer this question? Why? What change in score would make a difference to you and why?

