## **2 OBJECTIVES**

### **2.1 Primary**

To explore the symptom, impact and surgery experience of patients with severe, recurrent nasal polyps and obtain patient feedback regarding the adequacy of the SNOT-22 and GSK VAS assessments (in terms of relevance and comprehensiveness) in assessing disease experience in nasal polyps.

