### **2.2 Secondary**

#### **Combined concept elicitation (CE) and cognitive debriefing (CD) interviews:**

To identify through open-ended questioning the concepts that are important to patients with severe, recurrent, nasal polyps, who have been treated with surgery and the language they use to describe their disease experience. The main areas of exploration will be the symptoms with particular attention paid to the frequency, severity, duration and bother of each symptom, patients' surgical decision-making and surgical/treatment experience and the functional and HRQoL impact experienced by patients.

To cognitively test and explore the content and face validity of existing PRO instruments (single item VAS and SNOT-22) via assessment of the relevance and appropriateness of the items included in the instruments and the participants' ability to read, and consistently understand the instrument item wording, instructions, response option and recall period. The CD interviews will:

- Explore participants' ability to read and consistently understand the item wording, instructions, response options and recall period of the overall and single item VAS and SNOT-22.
- Explore the relevance and appropriateness of all of the items covered by the instruments based on the symptom experience of patients with nasal polyps.
- Verify if the key concepts identified in the concept elicitation phase of the study are adequately assessed by the PRO instruments (confirmation of face validity) and if any gaps exist, provide recommendations for how these could be addressed.
- Explore what level of change in symptoms and/or impacts the patients might consider meaningful. (E.g. what level of change they might consider noticeable and important in response to treatment, and how changes on the item scores might relate to changes in their experience in their symptoms and/or functional impacts.

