**Using the interview guide**

Throughout this guide we have coded the questions and instructions so that it is clear which questions are required and which are probes and do not necessarily need to be asked. The code is as follows:

Blue font	These are instructions to you
	These are statements that you are to read aloud word-for-word
1.	Questions prefixed by a specific number must be posed to all patients
•	All probes are bulleted – these do not need to be used specifically but are included to assist you in drawing further information from the patients

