**26. Is there anything else you would like to tell me about your nasal polyps that we haven't already discussed?**

## 27. Think aloud cognitive debriefing (60 minutes)

---

**[TO INTERVIEWER]** Ask the participant to read **aloud** the instructions, each item and the responses they choose for each questionnaire. After the participant has responded to each item ask the participant the corresponding questions in the table below. Ask the participant to complete **all** of the questions.

- 💡 *“For each instruction and question of each of the following questionnaires, I want you to read it out loud, and tell me what you are thinking when you are answering. Please tell me any thoughts or opinions you have on the instructions and questions as you read them and tell me why you selected the answer you did.”*
- 💡 *“After you respond to each question I am going to ask you some questions about each instruction/item. These will be about your understanding of the item and its relevance to your experience with nasal polyps. Additionally, I will ask you about the response options you selected for each assessment and what it would mean to you to select a different response option.”*
- 💡 *“You may decline to answer any question”*
- 💡 *“The questions I ask may be a bit repetitive, but they are important so that we can see how you understand each question.”*

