
In your own words, what is this instruction asking you to do? What does “social/emotional consequences” mean to you? What does “rhinosinusitis” mean to you? What does “problems” in relation to your condition mean to you?
		
What does “over the past two weeks mean to you”? How easy or difficult is it to remember your symptoms over the last two weeks? Do you think that it is appropriate to answer questions about your nasal polyps thinking back to the past two weeks? Tell me about that.
	

[INSTRUCTION 2] Considering how severe the problem is when you experience it and how often it happens, please rate each item below on how “bad” it is by selecting the number that corresponds with how you feeling using this scale.
			

In your own words, what is this instruction asking you to do? What does “severe” mean to you? What does “how bad” mean to you? What does “how often it happens” mean to you? What does “corresponds with how you are feeling” mean to you?
	
Based on your experience of nasal polyps, do you think that how bad your symptoms are (severity) and how often you experience a symptom (frequency) can be assessed at the same time? Are they the same or different? Why?
		
How would you describe: “No problem” “Very Mild Problem” “Mild or Slight Problem” “Moderate Problem” “Severe Problem” “Problem as bad as it can be”

[QUESTION 1] Need to blow nose
			

What does “need to blow nose” mean to you? Would you use any other words to describe this symptom?
	
Do you experience this as part of your nasal polyps? Why did you choose an answer of [X]? Would your score be different if you were asked to rate the severity and frequency of your “need to blow nose” separately, rather than together? Why?
	
What time frame were you thinking about when answering this question? Was it easy or difficult to remember over the past 2 weeks? Did you think about both how bad the symptom is and how often you experience it? Why/Why not?
	
How easy or difficult was it for you answer this question? Why? What change in score would make a difference to you and why?

ADELPHI VALUES

Understanding	Relevance	Recall period	Response Options
	What would your severity based and frequency based scores be?		
[QUESTION 2] Nasal blockage			

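### Both ease-of-recall probes for the 24-hour VAS items ask about two weeks, and no mandatory question asks patients what the VAS set leaves out

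*Combined protocol and SAP*

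**What the plan says.** Section 2.1 (primary objective) sets out to "obtain patient feedback regarding the adequacy of the SNOT-22 and GSK VAS assessments (in terms of relevance and comprehensiveness". Section 2.2 adds that the debriefing will explore understanding of the "response options and recall period of the overall and single item VAS and SNOT-22".

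The debriefing itself is laid out in Appendix 7. Interviewers are told: "After the participant has responded to each item ask the participant the corresponding questions in the table below". The guide's key separates bulleted probes, which are optional, from numbered questions: "Questions prefixed by a specific number must be posed to all patients".

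**SNOT-22.** Its instruction sets a two-week recall. The probes for Instruction 1 ask "How easy or difficult is it to remember your symptoms over the last two weeks" and also "Do you think that it is appropriate to answer questions about your nasal polyps thinking back to the past two weeks". After the items, Q28 to Q30 ask for general views, for missing symptoms or impacts (Q29), and for further comments.

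**VAS.** All six items refer to the previous 24 hours. The Recall period column is filled for two of them, nasal obstruction and mucus in the throat. Both entries ask which time frame the patient had in mind, and then "Was it easy or difficult to remember over the past 2 weeks". After the items come Q31 (views of the scales in general) and Q32 (further comments).

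**The concern.** The two-week probe is right for the SNOT-22 and appears to have been carried into the VAS table unchanged. No VAS item uses a two-week period, so no reading makes it right there. If the probe is used as worded, it collects answers about a period the scales do not ask about, and ease of recall over the actual period goes unprobed. It could also unsettle a patient's sense of the time frame for later VAS items.

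The second gap concerns comprehensiveness. The primary objective names it for both instruments, but only the SNOT-22 has a mandatory question on what is missing. That question comes under SNOT-22 feedback, before the VAS are debriefed.

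Appendix 7 describes these scales as proposed for the sponsor's phase III trial, and Section 1 says that such items were not historically built from patient input. Section 4 lists content validity of the reviewed instruments among the intended outputs. The gaps therefore fall on evidence the study was set up to collect.

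**Working it through.** The plan states no figure on this point, so the check is a comparison of the two halves of the debriefing guide in Appendix 7, with counts.

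| Feature | SNOT-22 | VAS |
|---|---|---|
| Recall period of the instrument | two weeks (14 days) | 24 hours (1 day), 6 of 6 items |
| Ease-of-recall probes | 6 (Instruction 1; items 1, 5, 10, 13, 21) | 2 (nasal obstruction; mucus in throat) |
| Of these, naming the instrument's own period | 6 of 6 | 0 of 2 |
| Probe on whether the period is appropriate | yes (Instruction 1) | none |
| Numbered question on missing content | 1 (Q29) | 0 (Q31 and Q32 do not ask it) |

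Across both instruments there are 6 + 2 = 8 ease-of-recall probes. Eight name two weeks and none names 24 hours.

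**What the VAS section does ask about the 24-hour period**
- What the period means to the patient: 1 of 6 items (nasal obstruction).
- Which time frame the patient used: 2 of 6 (nasal obstruction, mucus in throat).
- Whether severity varies over 24 hours: 3 of 6 (nasal obstruction, mucus in throat, loss of smell).
- How easy the item was to answer, without reference to recall: 6 of 6.

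Understanding of the period is thus partly covered. Ease of 24-hour recall and its appropriateness have no probe of their own.

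**Whether another numbered question fills the comprehensiveness gap**
- Q9 and Q26 are mandatory but ask about the disease, not about the scales.
- Q29 is mandatory but refers to the SNOT-22.
- Q31 parallels Q28, and Q32 parallels Q30. For the SNOT-22 the authors added Q29 to that same pair; for the VAS they did not.

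For context, the VAS set has 5 single-symptom items and 1 overall item. The guide's own symptom list has 11 + 16 = 27 entries. The list contains overlapping terms, so the comparison does not measure a content gap.

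**Two small wording slips in the same tables.** The overall VAS asks for a preference against the preceding question, which is the facial pain or pressure item and not an alternative wording. One probe for SNOT-22 item 22 (Embarrassed) refers to sadness.

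**The case against.** The strongest reply is that the guide is not a script. Section 3.3 says it need not be read verbatim and requires interviewers to be briefed on it. Appendix 7 lets them reword probes and says that not every probe need be used. On that view the two-week wording is a copying slip in an optional probe.

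The 24-hour coverage can also be read more generously. All six items use the same phrase, so asking its meaning once is reasonable, as is done for the SNOT-22. The time-frame probe would reveal a patient using the wrong window. Lasting confusion is unlikely, because probes follow the response and each item restates 24 hours and is read aloud.

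On comprehensiveness, there is a good deal of indirect patient evidence. Q8 to Q12 cover listed and further symptoms and ask which are worst, most frequent and most bothersome. Every SNOT-22 item carries a relevance probe, and those items include counterparts of all five VAS symptoms. A symptom named as missing at Q29 would therefore usually be missing from the single-symptom VAS too. Section 2.2 also commits the researchers to "Verify if the key concepts identified in the concept elicitation phase of the study are adequately assessed by the PRO instruments", and Q32 is an open invitation that every patient receives.

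Much of this stands, and it lowers the consequence. It does not remove the point. Discretion to repair a wrong probe does not ensure that it is repaired. A researcher's comparison of concepts with items can show gaps, but it is not the patient's own judgement of whether the VAS set is sufficient, which is what the primary objective asks for. The objection that the interview is already full is fair and is taken up under the fix.

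**Conclusion.** The concern holds. The recall probe is wrong as written in 2 of 2 places where it appears for the VAS (14 days against 1 day). The mandatory missing-content question exists for the SNOT-22 and not for the VAS (1 against 0). The conclusion is limited: direct, standardised patient feedback on ease of 24-hour recall and on gaps in the VAS set is not ensured. It may still arise through interviewer rewording, Q32 or the indirect evidence.

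No numerical result, sample size or analysis is affected. The correction should be made because it is nearly free and bears on a stated objective. Feedback not collected at interview could be recovered only by contacting participants again. The two wording slips are proofreading matters and add little weight.

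**What to change.** In Appendix 7:

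1. In the Recall period column for the nasal obstruction and mucus in throat VAS, replace the two-week reference in the ease-of-recall probe with the previous 24 hours.
2. After Q31, add a numbered question mirroring Q29, asking whether any symptoms or impacts of the patient's nasal polyps are missing from this set of scales. Renumber what follows.
3. Minor: in the overall VAS, name the intended comparator for the wording-preference probe, or delete the probe.
4. Minor: in SNOT-22 item 22, make the severity-and-frequency probe refer to embarrassment.

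A VAS counterpart to the SNOT-22 probe on whether the recall period is appropriate would be a sensible optional addition; it is not costed here.

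Cost: wording changes plus one question, with no change to sample, eligibility or analysis. Assuming 1 to 2 minutes per interview, the total is 30 × 1 = 30 to 30 × 2 = 60 minutes over 30 interviews. As a share of the 60-minute debriefing section, that is 1/60 = 1.7% to 2/60 = 3.3%. The schedule already sums to 5 + 55 + 60 = 120 minutes, and participants who do the app task first answer further questions at the end. The added time would therefore have to be absorbed, for example by using fewer optional probes.
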